9.5 For phase 2 protocols only: Reporting and Exclusions

9.5.1 Evaluation of Toxicity

All patients will be evaluable for toxicity from the time of their first treatment with pinometostat.

9.5.2 Evaluation of Response

All patients included in the study must be assessed for response to treatment, even if there are major protocol treatment deviations or if they are ineligible. Each patient will be assigned one of the following categories: 1) complete response, 2) partial response, 3) stable disease, 4) morphologic leukemia-free state, 5) early death from malignant disease, 6) early death from toxicity, 7) early death because of other cause, 8) progressive disease, or 9) unknown (not assessable, insufficient data). [Note: By arbitrary convention, category 9 usually designates the “unknown” status of any type of data in a clinical

database.]

All of the patients who met the eligibility criteria (with the possible exception of those who received no study medication) should be included in the main analysis of the response rate. Patients in response categories 5-9 should be considered to have a treatment failure (disease progression). Thus, an incorrect treatment schedule or drug administration does not result in exclusion from the analysis of the response rate. Precise definitions for categories 4-9 will be protocol specific.

All conclusions should be based on all eligible patients. Subanalyses may then be performed on the basis of a subset of patients, excluding those for whom major protocol deviations have been identified (*e.g.*, early death due to other reasons, early discontinuation of treatment, major protocol violations, etc.). However, these subanalyses may not serve as the basis for drawing conclusions concerning treatment efficacy, and the reasons for excluding patients from the analysis should be clearly reported. The 95% confidence intervals should also be provided.

9.6 Early Stopping Criteria

The study includes sequential stopping rules to monitor for safety in the phase II study after safety has been confirmed in the first six patients. These rules are based on the 30 patients who will accrue after the safety run-in. The toxicity definitions for these rules mirror the DLT definition. In the event that three in the first six patients, five in the first 12 patients, six in the first 18 patients, seven in the first 24 patients, or eight patients at any point among the remaining 30 patients fulfill the toxicity criteria, accrual to the study will stop due to a lack of safety. If the true risk of toxicity is 15%, the probability the intervention will be ruled unsafe is 10%. If the true risk increases to 40%, the probability increases to 95%.

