Correlative studies will include morphology, flow cytometry, cytogenetics, and a myeloid genetics panel, all of which are standard of care. These will be performed on bone marrow biopsy samples taken at each time point - prior to therapy initiation and at the end of cycle 1 for the phase Ib, and prior to therapy initiation, end of cycle 1, end of cycle 3, end of cycle 6 and / or after therapy cessation for the phase II. Specimen collection for these assays will be mandatory. Integral biomarkers for identification of 11q23 / MLL rearrangements would be performed as part of these assessments. The assays will be performed at MSKCC or local CLIA-certified pathology laboratories, which have experience processing samples from patients with leukemia.

Additionally, we seek to study changes in methylation patterns with the use of this combination. This is important for understanding on-target effects as MLL-rearranged leukemia is driven by hypermethylation, and pinometostat works to inhibit DOT1L methyltransferase activity and 5-azacytidine is a DNA hypomethylating agent. The assay of choice would be an ELISA assay to quantitate the extent of H3K79 methylation in leukemia cells, performed on mandatory samples from bone marrow samples identified above. The ELISA would be performed in [name] lab at DFCI, which has extensive experience with this assay.

The ELISA would not be a CLIA-certified test and would be solely performed for research purposes as part of an integrated biomarker. Samples would be viably cryopreserved at each institution and shipped to the study coordinator MSKCC for storage. At the end of the study, the samples would be shipped to DFCI, care of [name] laboratory, and the assay would be batch run on all samples.

As the mechanism of leukemogenesis in MLL-rearranged leukemia relies on hypermethylation of H3K79 by DOT1L, leading to increased transcription of HOXA9 and Meis1, we anticipate that expression levels of these two genes will decrease with treatment. As such, we plan to use qPCR to evaluate gene expression level prior to treatment on mandatory bone marrow samples at the time points identified above. The qPCR assays will be run in the [name] lab at DFCI, which has extensive experience running these qPCR assays. This would not be a CLIA-certified

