The MTD is defined as the dose level below which >1 patient out of 3 or ≥ 2 patients out of 6 experience a DLT. The second dose level may begin accrual only if all patients at the first dose level have been observed for a minimum of 28 days, i.e. through the first 28-day cycle. However, if at Day 28 the patient has Grade 3 or 4 neutropenia or thrombocytopenia, (not attributable to persistent leukemia; see DLT definition below), the patient will not begin Cycle 2 and must be observed until Day 42 in order to determine whether a DLT has occurred. In this instance, dose escalation cannot proceed until at least Day 42 so that resolution may be assessed. If patients do not fulfill the definition of severe myelosuppression at Day 28, or if they recover between Days 28 and 42, no hematological DLT will be deemed to have occurred. Patients may then proceed to cycle 2 for further treatment of persistent disease or in the setting of a response.

Once the MTD is reached, the cohort at the MTD will be expanded in the phase II portion of the trial.

A DLT will be defined as a significant suspected adverse reaction or clinically significant abnormal laboratory value assessed as unrelated to disease progression, intercurrent illness, or concomitant medications (only AEs that are incontrovertibly due to an extraneous cause will be excluded as a DLT) and of onset within the first 28 days on study that meets any of the following criteria:

- Any Grade 5 toxicity
- Grade 4 neutropenia lasting ≥ 42 days from start of cycle in absence of evidence of active leukemia

- Any Grade \geq 3 non-hematologic toxicity not clearly resulting from the underlying leukemia EXCEPT:
 - Alopecia
 - Grade 3 fatigue, asthenia, fever, anorexia, or constipation
 - Grade 3 nausea, vomiting, or diarrhea not requiring tube feeding, total parenteral nutrition, or requiring or prolonging hospitalization
 - Infection, bleeding, or other expected direct complication of cytopenias due to active underlying leukemia
 - Grade 3 infusion reaction including cytokine release syndrome, if successfully managed and which resolves within 72 hours
 - Grade 3 or 4 tumor lysis syndrome if it is successfully managed clinically and resolves within 7 days without end-organ damage
 - Grade 3 or 4 isolated electrolyte abnormalities (i.e., those occurring without clinical consequence) that resolve, with or without intervention, to less than Grade 2 in less than 72 hours will not be considered DLT

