- Response to combination therapy defined as CR, CRi, PR, or MLFS, with or without minimal residual disease (MRD), on bone marrow biopsy as defined by the 2017 European Leukemia Network guidelines will be assessed. Baseline bone marrow biopsy will be performed within 14 days prior to starting therapy, at the end of cycle 1 (day 28 +/- 2 days or time of count recovery), at the end of cycle 3 (+/- 2 days or at the time of count recovery after three cycles of azacitidine administration), at the end of cycle 6 (+/- 2 days or at the time of count recovery after six cycles of azacitidine administration), and / or at the time of therapy discontinuation +/- 3 days. Patients who have stable disease after 4 cycles of combination therapy or progressive disease at any time should be taken off the trial.

Phase II Primary Endpoint Analytic Plan:

- Response rate will be defined as the number of patients who achieve a CR, CRi, PR, or morphologic leukemia-free state (MLFS), with or without MRD, at any time point. Patients will be evaluated through the time of count recovery after 6 cycles of combination therapy.
- A Simon two-stage minimax design will be employed whereby a 20% response rate is considered not promising, a 40% response rate is considered promising, and the probabilities of a type I error (falsely accepting a non-promising therapy) and type II error (falsely rejecting a promising therapy) are set at 0.10 and 0.10, respectively. In the first stage of this design, 19 patients will be accrued. All patients will be followed for a minimum of 24 weeks. If at least 4 patients respond then an additional 17 patients will be accrued to the second stage. At the end of the trial, if 11 or more patients respond out of a total of 36 patients, then this combination will be considered worthy of further investigation. This design yields at least a 0.90 probability of a positive result if the true response rate is at least 40% and yields a 0.90 probability of a negative result if the true response rate is 20%.

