9.2 Sample Size/Accrual Rate

Maximum planned sample size is 48 patients, with estimated monthly accrual rate of 3-6 patients among all sites per month.

PLANNED ENROLLMENT REPORT

Racial Categories	Ethnic Categories				Total
	Not Hispanic or Latino		Hispanic or Latino		
	Female	Male	Female	Male	
American Indian/ Alaska Native	0	0	0	0	0
Asian	2	2	0	0	4
Native Hawaiian or Other Pacific Islander	0	0	0	0	0
Black or African American	3	4	0	0	7
White	8	9	2	2	21
More Than One Race	2	2	0	0	4
Total	15	17	2	2	36

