13.1 Study Oversight

This protocol is monitored at several levels, as described in this section. The Protocol Principal Investigator is responsible for monitoring the conduct and progress of the clinical trial, including the ongoing review of accrual, patient-specific clinical and laboratory data, and routine and serious adverse events; reporting of expedited adverse events; and accumulation of reported adverse events from other trials testing the same drug(s). The Protocol Principal Investigator and statistician have access to the data at all times through the CTMS web-based reporting portal. For the Phase 1 portion of this study, all decisions regarding dose escalation/expansion/de-escalation require sign-off by the Protocol Principal Investigator through the CTMS/IWRS. In addition, for the Phase 1 portion, the Protocol Principal Investigator will have at least monthly, or more frequently, conference calls with the Study Investigators and the CTEP Medical Officer(s) to review accrual, progress, and adverse events and unanticipated problems.

For a Phase 1/2 trial, enrollment to the Phase 2 portion of the trial will not begin until a protocol amendment has been submitted which summarizes the Phase 1 results, the recommended Phase 2 dose, and the rationale for selecting it. The amendment must be reviewed and approved by CTEP before enrollment to the Phase 2 portion can begin.

During the Phase 2 portion of the study, the Protocol Principal Investigator will have, at a minimum, quarterly conference calls with the Study Investigators and the CTEP Medical Officer(s) to review accrual, progress, and pharmacovigilance. Decisions to proceed to the second stage of a Phase 2 trial will require sign-off by the Protocol Principal Investigator and the Protocol Statistician.

All Study Investigators at participating sites who register/enroll patients on a given protocol are responsible for timely submission of data via Medidata Rave and timely reporting of adverse events for that particular study. This includes timely review of data collected on the electronic CRFs submitted via Medidata Rave.

All studies are also reviewed in accordance with the enrolling institution's data safety monitoring plan. A central data safety monitoring board consisting of study team members will hold a conference, approximately once per week, to discuss safety issues that arise with the trial.

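### The plan does not say whether run-in patients treated at the phase II dose count in the 19 and 36 of the Simon design, and the stated 10% false-stop probability of the safety rule is not reproduced for 30 or for 36 patients

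*Combined protocol and SAP*

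**What the plan says.** - **Section 9.1** sets a Simon two-stage design with 19 patients, then 17 more if at least 4 respond. The combination is judged worth pursuing "if 11 or more patients respond out of a total of 36 patients".
- **Section 9.6** applies its safety rule in phase II "after safety has been confirmed in the first six patients", and adds: "These rules are based on the 30 patients who will accrue after the safety run-in". Accrual stops at "three in the first six patients, five in the first 12 patients, six in the first 18 patients, seven in the first 24 patients", or at eight among the 30. The stated probability of stopping is 10% at a true toxicity risk of 15%, and 95% at 40%.
- **Section 9.2** states: "Maximum planned sample size is 48 patients". The Planned Enrollment Report below it totals 36.
- **Section 7** points towards counting the run-in: "Once the MTD is reached, the cohort at the MTD will be expanded in the phase II portion of the trial".
- **Sections 6.3 and 13.1** can be read the other way. Section 6.3 says there will be no expansion cohort and that patients will join the phase II study at the recommended dose. Section 13.1 says that "enrollment to the Phase 2 portion of the trial will not begin until a protocol amendment has been submitted".
- **Section 5.1** lists correlative marrow samples "prior to therapy initiation and at the end of cycle 1 for the phase Ib", and adds later time points only for phase II.

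**The concern.** The plan leaves open who is in the primary analysis. The 4-of-19 and 11-of-36 decisions are go/no-go counts. If the six run-in patients at the phase II dose may be included or left out, two analysts could reach different counts from the same data, and the choice could be made after the run-in responses are known.

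The same choice fixes how many patients the safety rule must cover and what its error rates are. It also fixes the maximum size of the trial. The stated stopping probabilities therefore needed checking for both 30 and 36 patients.

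**Working it through.** **Inputs.** Safety boundaries 3/6, 5/12, 6/18, 7/24 and 8/30, with stated stopping probabilities of 10% at 15% toxicity and 95% at 40% (9.6). Simon design 4/19 then 11/36, with response rates of 20% and 40% (9.1). Maximum of 48 and table total of 36 (9.2). Dose levels and 3+3 rules (6.1, 6.2, 7, 9.1).

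**1. Efficacy design.** P(positive) = sum over x = 4 to 19 of P(X1 = x) × P(X2 ≥ 11 − x), where X1 ~ Bin(19, p) and X2 ~ Bin(17, p). This is 0.086 at p = 0.20 and 0.902 at p = 0.40. An exhaustive search confirms 19/36 as the minimax design, so the efficacy design is sound for 36 patients.

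**2. Safety rule as printed, 30 patients.** Let f(k, e) be the probability of e toxicities among k patients with no boundary yet crossed. Then f(k, e) = (1 − p)·f(k−1, e) + p·f(k−1, e−1). At each look, the mass at or above the boundary is removed and added to the stopping probability. Cumulative stopping probability:

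| After patient | p = 0.15 | p = 0.40 |
|---|---|---|
| 6 | 0.047 | 0.456 |
| 12 | 0.058 | 0.633 |
| 18 | 0.079 | 0.822 |
| 24 | 0.101 | 0.921 |
| 30 | **0.122** | **0.966** |

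Monitoring after every patient gives the same totals, and a simulation of 400,000 trials agrees. The stated 95% is close to 96.6%. The stated 10% is low by 2.2 percentage points. Without the six-patient look the rule gives 0.0975 and 0.9635, so the stated figures look like 30-patient figures for a slightly different set of looks.

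**3. Same recursion, 36 phase II patients.** The plan gives no boundary beyond 30, so these extensions are illustrative.

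| Extension | p = 0.15 | p = 0.40 |
|---|---|---|
| Limit of 8 carried to 36 | 0.195 | 0.993 |
| Printed limits plus 9 of 36 | 0.142 | 0.985 |

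**4. Counting patients.** A 3+3 run-in over two dose levels uses at most 6 + 6 = 12. The path 54, 90, back to 54, then 36 mg/m²/day uses up to 6 + 6 + 6 = 18.

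| Reading | Two levels | Three levels |
|---|---|---|
| Run-in at phase II dose counted (30 more) | 12 + 30 = 42 | 18 + 30 = **48** |
| Not counted (36 more) | 12 + 36 = **48** | 18 + 36 = 54 |

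The stated maximum of 48 fits one cell in each row, so it cannot show which reading is meant.

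**5. Enrolment table.** 15 + 17 + 2 + 2 = 36, which is 12 below the stated maximum (12/48 = 25%).

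**The case against.** The strongest reply is that one reading fits the main figures. If six run-in patients at the phase II dose count, then 6 + 30 = 36 and 18 + 30 = 48. Section 7 speaks of expanding the cohort, and Section 9.6 places its rule after the first six patients. The Section 13.1 sentence is general text on when phase II may open and does not say whose data are analysed. Section 6.3 is compatible with adding patients to the run-in cohort. This stands. A reader might infer that 9.1, 9.2 and 9.6 cannot describe one trial, but the documents do not support that. What remains is that the reading has to be assembled from several sections and is nowhere stated. The sum of 18 + 30 also assumes that phase II could run at level −1.

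Three other inferences go too far:

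- **Response bias.** One might conclude from Section 5.1 that run-in patients are assessed on a shorter schedule. That list concerns correlative samples and is an outlier. Elsewhere Section 5.1 has cycle 3 and end-of-treatment marrows for both phases, and its specimen table makes no phase distinction. The calendar (Section 11) and Section 12 set assessments at the end of cycles 1, 3 and 6, also without separating the phases.
- **Unmonitored patients.** Section 6.3 has real-time toxicity review, and Section 13.1 a roughly weekly safety conference. On the 36-new-patients reading, six would lack a formal boundary, not monitoring.
- **19.5% as the plan's error rate.** Section 9.6 confines the limit of 8 to 30 patients, so this figure describes an extension that the plan does not propose. The like-for-like change is from 12.2% to 14.2% with a 9-of-36 limit.

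The enrolment table may be meant for phase II only, but it is not labelled so.

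**Conclusion.** The concern holds as an unstated denominator together with safety figures that do not reproduce. The text leans towards counting the run-in patients but does not settle it. If they count, the rule covers the right 30 patients, but its false-stop probability is 12.2% and not 10%. If they do not, the rule stops six patients short of 36, and any extension needs its own figures: 14.2%/98.5% or 19.5%/99.3% in the two examples. The maximum would then be 48 or 54. The table and the stated maximum differ by 12 whichever reading is taken.

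These results assume independent patients with a constant toxicity risk, and at most six patients per run-in dose level. The efficacy design itself is not in question.

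**What to change.** In the amendment that Section 13.1 already requires before phase II:

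1. State in 9.1, 9.2 and 9.6 whether run-in patients at the phase II dose count in the 19 and the 36. Fix this before their responses are used, and align 6.3 and Section 7 with it.
2. Make the patient number in 9.6 match. If it is 30, restate the stopping probabilities as 12.2% and 96.6%. If it is 36, the sponsor chooses the boundary to 36 and recomputes both probabilities for it.
3. Show in 9.2 how the maximum is built up, including level −1, and make the Planned Enrollment Report agree with it.
4. Reconcile the phase Ib marrow time points within Section 5.1 and with Sections 11 and 12.

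The cost is wording and recalculation. No patients are added beyond those that the chosen reading already implies.

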9. STATISTICAL CONSIDERATIONS

9.1 Study Design/Endpoints

Phase Ib Safety / Tolerability Run In - Primary Endpoint:

- Safety and tolerability will be assessed by evaluating the number of patients out of 6 who experience a dose-limiting toxicity by cycle 1, day 42, using a standard 3+3 design. Two out of 6 events will lead to a dose-reduction or trial discontinuation as described in the analytic plan.

Phase Ib Safety / Tolerability Run In - Primary Endpoint Analytic Plan:

- An incidence of one in six (or fewer) patients experiencing a DLT, as described in section 7, will be considered a safe and tolerable dose.
- Patients who receive at least a full course of therapy will be considered to be evaluable for toxicity/DLT and will not be replaced unless the PI determines that further additional patients at that dose level are required for safety purposes. Patients who experience a DLT prior to completing a full course of therapy will be accounted for in the safety assessment.
- A standard 3+3 design will be used to study patients on an initial pinometostat dose of 54 mg/m²/day continuous IV infusion, in combination with azacitidine at a dose of 75mg/m² daily for 7 days starting on cycle 1, day 1. If two of six experience a DLT within the first 42 days as defined above, the dose of pinometostat will be decreased to 36 mg/m²/day, and it will be combined with azacitidine at a dose of 75mg/m² daily for 7 days in a separate cohort of patients. If two of six experience a DLT within the first 42 days as defined above, the combination will be deemed intolerable and the study will be terminated. If three patients tolerate the combination of standard-dose azacitidine with pinometostat at 54 mg/m²/day, the pinometostat dose may be escalated to 90 mg/m²/day and tested as per standard 3+3 design. Patients who complete cycle 1 would be allowed to stay on single-agent pinometostat through their day 42 evaluation. Patients who achieve count recovery prior to day 42 may be considered for additional combination therapy with azacitidine and may complete up to 6 cycles of combination therapy as described for patients directly enrolled on the phase II protocol.

Phase II Primary Endpoint:

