12.1.1 Definitions

Evaluable for toxicity. All patients will be evaluable for toxicity from the time of their first treatment with pinometostat.

Evaluable for objective response. Only those patients who have measurable disease present at baseline, have received at least one cycle of therapy, and have had their disease re-evaluated will be considered evaluable for response. These patients will have their response classified according to the definitions stated below. (Note: Patients who exhibit objective disease progression prior to the end of cycle 1 will also be considered evaluable.)

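### Section 9.6 does not define the denominator of the phase II safety rule; read with 9.5.1, patients who leave cycle 1 early without a DLT count as non-events, which can lower the chance of stopping

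*Combined protocol and SAP*

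**What the plan says.** - **Rule (9.6).** The early limits read: "In the event that three in the first six patients, five in the first 12 patients, six in the first 18 patients". The later limits are 7 of 24, and 8 at any time up to patient 30. Reaching any limit halts accrual. On size: "These rules are based on the 30 patients who will accrue after the safety run-in". The events follow the DLT definition. The stated probability of stopping is 10% at a true risk of 15% and 95% at a true risk of 40%.
- **Phase Ib evaluability (9.1).** "Patients who receive at least a full course of therapy will be considered to be evaluable for toxicity/DLT". A DLT before the course is complete also counts.
- **Phase II evaluability (9.5.1, repeated in 12.1.1).** "All patients will be evaluable for toxicity from the time of their first treatment with pinometostat".
- **DLT definition (7).** Onset falls in the first 28 days. The neutropenia criterion runs to 42 days from cycle start and requires no evidence of active leukemia. Events due to disease progression are excluded.
- **Follow-up (6.6).** One month after removal from study, or until death.
- **Early departure is foreseen.** Progression takes a patient off study (6.5), and 9.5.2 has three early-death categories. Section 12.1.1, on response, adds: "Patients who exhibit objective disease progression prior to the end of cycle 1 will also be considered evaluable".

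Section 9.6 does not say how a patient who leaves cycle 1 without a DLT is treated in the count.

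**The concern.** The event in 9.6 is borrowed from phase Ib, but the rule for who counts is not. The only denominator the plan gives for phase II toxicity is all treated patients. On that reading, a patient who progresses in week 2 with no DLT takes one of the places in the first six or first 12 and contributes a non-event, although most of the cycle was never given. If the 15% and 40% in 9.6 are full-cycle risks, as in phase Ib, such patients can only pull the observed event rate down.

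This is the only numerical toxicity boundary in phase II, and who occupies each look decides whether accrual stops. The question should not be left to be settled mid-trial with the events in view. Phase Ib and phase II DLT rates would also rest on different denominators.

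**Working it through.** **Inputs from 9.6.** Stop at 3 of 6, 5 of 12, 6 of 18, 7 of 24, or 8 at any point among 30; true risks 15% and 40%.

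**Assumptions.** A share f of accrued patients leaves cycle 1 early (the documents give no value, so 5% to 30% is shown). The 40% is a full-cycle risk. A full course in 9.1 means completing cycle 1.

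**Method.** Let S_i(k) be the probability that accrual is still open after i counted patients with k events, and θ the chance that a counted patient has an observed event. Then S_0(0) = 1 and S_i(k) = (1−θ)·S_{i−1}(k) + θ·S_{i−1}(k−1). States at or above a boundary are removed and added to P(stop).

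**Step 1: the plan's own figures (f = 0).** θ = 0.40 gives P(stop) = 0.966, so the stated 95% reproduces with a small margin. θ = 0.15 gives 0.122 against the stated 10%. Variants tried (for example no eight-event limit: 0.101 and 0.921; only 8 of 30 at the end: 0.070 and 0.956) do not give both stated figures.

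**Step 2: leavers kept as non-events, 40% risk.** If all their toxicities go unseen, θ = 0.40(1−f). If half do, θ = 0.40(1−f/2).

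| f | θ, all unseen | P(stop) | θ, half unseen | P(stop) |
|---|---|---|---|---|
| 0 | 0.40 | 0.966 | 0.40 | 0.966 |
| 5% | 0.38 | 0.946 | 0.39 | 0.957 |
| 10% | 0.36 | 0.918 | 0.38 | 0.946 |
| 20% | 0.32 | 0.830 | 0.36 | 0.918 |
| 30% | 0.28 | 0.691 | 0.34 | 0.880 |

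**Step 3: break-even.** P(stop) = 0.95 at θ = 0.3833. The tolerable loss is 1 − 0.3833/0.40 = 4.2% of toxicities. That is f = 4.2% if all are unseen (1 of 30 is 3.3%, 2 of 30 is 6.7%) and f = 8.3% if half are (3 of 30 is 10%).

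**Step 4: 9.1 rule applied, 30 accrued, no replacement.** If all leavers' toxicities are unseen, the number evaluable is M ~ Binomial(30, 1−f), and P(stop) = Σ P(M = m) × P(stop in m patients at risk p).

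| f | 40% risk | 15% risk |
|---|---|---|
| 5% | 0.952 | 0.113 |
| 10% | 0.937 | 0.106 |
| 20% | 0.893 | 0.093 |
| 30% | 0.831 | 0.081 |

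**Step 5: side effect of that rule.** Leavers with an event enter the count and leavers without one do not. If half their toxicities are seen, the evaluable share is q = (1−f) + f·p/2 and the event rate among evaluable patients is p(1−f/2)/q. At p = 0.15 and f = 10% this is 0.1425/0.9075 = 0.157, and P(stop) = 0.125. At f = 30% it is 0.1275/0.7225 = 0.176, and P(stop) = 0.140. At p = 0.40 and f = 10% it is 0.38/0.92 = 0.413, and P(stop) = 0.957.

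**The case against.** A reader might infer that the plan declares early leavers toxicity-free and therefore fails to deliver its 95%. The documents support neither statement. Section 9.6 is silent on leavers; their treatment follows only from reading it with 9.5.1, a general sentence on evaluability. With no leavers the rule exceeds 95%, and no document figure says how many will leave.

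Four further points favor the plan:

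- **Follow-up.** A living patient removed in week 1 or 2 is due to be followed beyond day 28, so later-onset DLTs can be recorded. This stands, and it makes the all-unseen column a worst case. It does not remove the loss: follow-up does not restore the missed infusion, death ends it, and a patient leaving before about day 12 (42 − 30) finishes a month of follow-up before the 42-day neutropenia criterion can be judged. That criterion also cannot be met with active leukemia.
- **Early deaths.** Grade 5 toxicity is a DLT, and section 7 excludes only events that are incontrovertibly extraneous. Doubtful deaths therefore lean towards events; clear leukemic deaths do not.
- **Meaning of the risk.** If the true risk in 9.6 is per treated patient, matching 9.5.1, nothing is lost. This stands, but 9.6 does not say so, and it takes its events from a phase Ib definition with a different denominator.
- **Other oversight.** Real-time toxicity review (6.3) and roughly weekly safety conferences (13.1) reduce the consequence. They set no numerical boundary.

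**Conclusion.** The point holds as a gap with a conditional effect. Section 9.6 does not state its evaluable denominator, and the only one available for phase II differs from phase Ib. If leavers without a DLT fill look slots and the 40% is a full-cycle risk, the chance of stopping can only fall. The fall is small at 5% leavers (0.946 to 0.957 against 0.966) and material at 20% (0.830 to 0.918). It crosses below 95% once more than about 4% of toxicities go unseen. These figures rest on an assumed departure rate and an assumed share of unseen toxicities. They do not show that the trial will fall short of 95%.

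**What to change.** In 9.6, state that the looks at 6, 12, 18, 24 and 30 are counted in DLT-evaluable patients by the 9.1 rule: a patient enters the count on completing cycle 1 or on meeting the toxicity criteria, whichever comes first, and toxicity events always count. Keep 9.5.1 for general adverse event reporting. Leave boundaries and accrual unchanged. Restate the stop probabilities over a range of early departure, and correct the 10% at 15% risk, which recomputes to 12.2%.

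The cost is about one sentence plus the restated figures. Looks fall slightly later. Fewer than 30 patients may be evaluable (24 expected at 20% leavers in the worst case), so the rule improves P(stop) without guaranteeing 95%; securing 30 evaluable patients would need extra accrual. If leavers' toxicities are partly seen, the chance of stopping at 15% risk rises slightly, as in step 5.

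If the team prefers to count all treated patients, 9.6 should say so and define the 15% and 40% as risks per treated patient.

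### Section 9.6 states a 10% chance of stopping at 15% toxicity, but the printed safety boundaries give 12.2%

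*Combined protocol and SAP*

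**What the plan says.** Section 9.6 (Early Stopping Criteria) defines the population for the rule: "These rules are based on the 30 patients who will accrue after the safety run-in". The event is binary per patient: "The toxicity definitions for these rules mirror the DLT definition". Accrual stops on "three in the first six patients, five in the first 12 patients, six in the first 18 patients, seven in the first 24 patients". A last boundary of eight events applies throughout the 30.

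The section then gives two operating characteristics. The first is "If the true risk of toxicity is 15%, the probability the intervention will be ruled unsafe is 10" percent. The second is "If the true risk increases to 40%, the probability increases to 95" percent. It mentions no other stopping mechanism in connection with these figures, and no other section restates or corrects them.

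**The concern.** The section supplies everything needed to check its own claim: the number of patients, the five boundaries, the two true risks and the two resulting probabilities. The probabilities should therefore follow from the boundaries, and the one at 15% does not.

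Two things are at stake. The 10% is the stated chance of wrongly halting a regimen whose toxicity is acceptable, so anyone relying on 9.6 understates that chance by about a fifth (12.2 / 10 = 1.22). Also, if the probability is right and a boundary is the misprint, accrual would be monitored against a rule nobody intended. Nothing in the documents says which of the two it is.

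**Working it through.** **Inputs, all from section 9.6.** There are 30 patients, taken as independent with a common toxicity risk p. Stop at ≥3 of 6, ≥5 of 12, ≥6 of 18, ≥7 of 24, or on the 8th event at any point. The values of p are 0.15 and 0.40.

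**Method.** Let f(n, x) be the probability that the rule has not stopped before look n and x events have occurred by then. Moving from one look to the next adds six patients:

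f(n+6, x) = Σ over surviving y of f(n, y) × C(6, x−y) p^(x−y) (1−p)^(6−x+y)

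At each look, the mass at or above the boundary is the probability of stopping there. It is removed before the next step.

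**First two looks at p = 0.15, by hand.**

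- Six patients: P(0) = 0.3771, P(1) = 0.3993, P(2) = 0.1762. The stop probability is 1 − 0.3771 − 0.3993 − 0.1762 = 0.0473 (from unrounded terms).
- Twelve patients: a path with 2 events needs at least 3 more, giving 0.1762 × 0.0473 = 0.0083. A path with 1 event needs at least 4 more, giving 0.3993 × 0.0059 = 0.0024. A path with none needs at least 5 more, giving 0.3771 × 0.0004 = 0.0002. The sum is 0.0108 (from unrounded terms).

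**Full result.**

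| Look | Boundary | Stop at this look, p = 0.15 | Cumulative | Stop at this look, p = 0.40 | Cumulative |
|---|---|---|---|---|---|
| 6 | 3 | 0.0473 | 0.0473 | 0.4557 | 0.4557 |
| 12 | 5 | 0.0108 | 0.0582 | 0.1771 | 0.6328 |
| 18 | 6 | 0.0203 | 0.0785 | 0.1896 | 0.8224 |
| 24 | 7 | 0.0221 | 0.1006 | 0.0986 | 0.9210 |
| 30 | 8 | 0.0213 | **0.1219** | 0.0449 | **0.9659** |

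A simulation of 2 million trials gives 0.1216 at 15% and 0.9659 at 40%. The printed rule gives 10% at a true toxicity of 14.2%, not 15%.

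**Block or continuous checking.** Event counts never fall, so a boundary reached inside a block of six is still reached at its end. A path that has survived the look at 24 has at most 6 events, so the eighth can only come in the last block. Checking at the looks or after every patient therefore gives the same 12.2%.

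**Other readings of the text.**

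| Reading | p = 0.15 | p = 0.40 |
|---|---|---|
| Boundaries read as more than, not at least | 4.0% | 91.6% |
| Final look only | 7.0% | 95.6% |
| Look at 6 patients omitted | 9.8% | 96.3% |
| Rule ends at 24 patients | 10.1% | 92.1% |

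The last two come near 10%, but both contradict the printed rule.

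**Could one misprinted boundary explain it?** These are diagnostic checks, not proposals. Using 4 instead of 3 at patient 6 gives 9.9% and 96.4%. Using 9 instead of 8 at patient 30 gives 10.4% and 94.5%. Of all 165 non-decreasing sets with each boundary shifted by −1, 0 or +1, none rounds to both 10% and 95%. The closest by total absolute difference is 3, 6, 6, 7, 9, with 10.2% and 94.4%.

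**The case against.** **The gap is small and cautious.** It is 2.2 points, the printed rule stops more often than stated, and sites act on the boundaries rather than on the 10%. This stands, and it makes the point low priority. It does not make 12.2% round to 10%.

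**A misprinted boundary is conjecture.** The boundaries rise smoothly, contradict nothing else, and no one-event change restores both figures exactly. That leans towards an approximate probability rather than a wrong boundary. It does not settle the matter, since two single-event changes bring the 15% figure close to 10%. The consequence for monitoring is therefore conditional.

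**The Simon futility stop in section 9.1 could lower the figure.** Assume response and toxicity are independent, and that futility ends accrual after 13 or 19 monitored patients (19 first-stage patients with or without six from the run-in). At a 20% response rate the 15%-toxicity figure is then 9.3% or 10.2%. The 40%-toxicity figure falls to 81.4% or 90.1%, well below 95%. At a 40% response rate the figures are 12.0–12.1% and 95.8–96.3%. None of these cases gives both stated values, and 9.6 mentions neither futility nor a response rate.

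**The base of 30 may not be the final one.** Section 9.1 plans 36 phase II patients and section 9.2 allows 48 in total. If 36 new patients were monitored with eight at any point, the rule would give 19.5% and 99.3%. This limits any replacement figure to the 30-patient base that 9.6 states. It moves further from 10%, so it does not rescue the printed value.

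**Conclusion.** The concern holds. As printed, the rule stops with probability 12.2% at 15% toxicity, against a stated 10%. At 40% it stops with probability 96.6% against a stated 95%, which is near enough not to count as a second error. The result is exact for the safety rule alone. It assumes 30 independent patients with a common risk, all of whom can accrue. It does not depend on how often toxicity is checked within the blocks. Whether the probability or a boundary is wrong cannot be determined from the documents. The effect is modest and on the cautious side.

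**What to change.** The sponsor should reconcile the boundaries in 9.6 with the stated probabilities.

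- If the boundaries are as intended, restate the probability at 15% toxicity as about 12%. For consistency, give the companion figure at 40% as about 97%.
- If a boundary is misprinted, correct it and report both probabilities recomputed exactly from the corrected rule.
- In either case, add a sentence saying that the figures are for the safety rule alone and assume all 30 patients accrue.

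The cost is two figures and one sentence, plus one boundary if that is where the misprint lies. The sample size is unaffected. Section 13.1 already requires a protocol amendment before phase II enrollment opens, so the correction can go in there.
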